12.3 Monitoring

Involvement in this study as a participating investigator implies acceptance of potential audits or inspections, including source data verification, by representatives designated by the Principal Investigator (or Protocol Chair) or DF/HCC. The purpose of these audits or inspections is to examine study-related activities and documents to determine whether these activities were conducted and data were recorded, analyzed, and accurately reported in accordance with the protocol, institutional policy, Good Clinical Practice (GCP), and any applicable regulatory requirements.

All data will be monitored for timeliness of submission, completeness, and adherence to protocol requirements. Monitoring will begin at the time of participant registration and will continue during protocol performance and completion.

13. REGULATORY CONSIDERATIONS

13.1 Protocol Review and Amendments

This protocol, the proposed informed consent and all forms of participant information related to the study (e.g., advertisements used to recruit participants) and any other

necessary documents must be submitted, reviewed and approved by a properly constituted IRB governing each study location.

Any changes made to the protocol must be submitted as amendments and must be approved by the IRB prior to implementation. Any changes in study conduct must be reported to the IRB. The Principal Investigator (or Protocol Chair) will disseminate protocol amendment information to all participating investigators.

All decisions of the IRB concerning the conduct of the study must be made in writing.

Any change or addition (excluding administrative) to this protocol requires a written protocol amendment that must be reviewed by Novartis and the investigator before implementation. Amendments significantly affecting the safety of subjects, the scope of the investigation or the scientific quality of the study require additional approval by the IRB at each study center. A copy of the written approval of the IRB must be provided to Novartis. Examples of amendments requiring such approval are:

1. Increases in drug dose or duration of exposure of subjects,
2. Significant changes in the study design (e.g. addition or deletion of a control group),
3. Increases in the number of invasive procedures,
4. Addition or deletions of a test procedure required for monitoring of safety.

These requirements for approval should in no way prevent any immediate action from being taken by the investigator or by Novartis in the interests of preserving the safety of all patients included in the trial. If an immediate change to the protocol is felt to be necessary by the investigator and is implemented for safety reasons Novartis must be notified and the IRB at the center must be informed immediately. Amendments affecting only administrative aspects of the study do not require formal protocol amendments or IRB approval but the IRB must be kept informed of such administrative changes. Examples of administrative changes not requiring formal protocol amendments and IRB approval include:

- Changes in the staff used to monitor trials
- Minor changes in the packaging or labeling of study drug.

13.2 Informed Consent

All participants must be provided a consent form describing this study and providing sufficient information for participants to make an informed decision about their participation in this study. The formal consent of a participant, using the IRB approved consent form, must be obtained before the participant is involved in any study-related procedure. The consent form must be signed and dated by the participant or the participant's legally authorized representative, and by the person obtaining the consent. The participant must be given a copy of the signed and dated consent document. The original signed copy of the consent document must be retained in the medical record or research file.

13.3 Ethics and Good Clinical Practice (GCP)

This study is to be conducted according to the following considerations, which represent good and sound research practice:

- ICH Consolidated Good Clinical Practice: Guidelines (E6)
www.fda.gov/cder/guidance/iche6.htm
- US Code of Federal Regulations (CFR) governing clinical study conduct and ethical principles that have their origin in the Declaration of Helsinki
 - Title 21 Part 11 – Electronic Records; Electronic Signatures
www.access.gpo.gov/nara/cfr/waisidx_02/21cfr11_02.html
 - Title 21 Part 50 – Protection of Human Subjects
www.access.gpo.gov/nara/cfr/waisidx_02/21cfr50_02.html
 - Title 21 Part 54 – Financial Disclosure by Clinical Investigators
www.access.gpo.gov/nara/cfr/waisidx_02/21cfr54_02.html
 - Title 21 Part 56 – Institutional Review Boards
www.access.gpo.gov/nara/cfr/waisidx_02/21cfr56_02.html
 - Title 21 Part 312 – Investigational New Drug Application
www.access.gpo.gov/nara/cfr/waisidx_02/21cfr312_02.html
- State laws
- Institutional research policies and procedures
www.dfhcc.harvard.edu/clinical-research-support/clinical-research-operations-cro/policies-and-procedures

It is understood that deviations from the protocol should be avoided, except when necessary to eliminate an immediate hazard to a research participant. In such case, the deviation must be reported to the IRB according to the local reporting policy.

13.4 Study Documentation

The investigator must prepare and maintain adequate and accurate case histories designed to record all observations and other data pertinent to the study for each research participant. This information enables the study to be fully documented and the study data to be subsequently verified.

Original source documents supporting entries in the case report forms include but are not limited to hospital records, clinical charts, laboratory and pharmacy records, recorded

data from automated instruments, microfiches, photographic negatives, microfilm or magnetic media, and/or x-rays.

13.5 Records Retention

All study-related documents must be retained for the maximum period required by applicable federal regulations and guidelines or institutional policies.

13.6 Multi-center Guidelines

This protocol will adhere to the policies and requirements of the Dana-Farber/Harvard Cancer Center. The specific responsibilities of the Principal Investigator (or Protocol Chair), Coordinating Center, and Participating Institutions are presented in the Dana-Farber/Harvard Cancer Center Multi-Center Data and Safety Monitoring Plan (see Appendix D).

- The Principal Investigator/Coordinating Center is responsible for distributing all IND Action Letters or Safety Reports to all participating institutions for submission to their individual IRBs for action as required.
- Mechanisms will be in place to ensure quality assurance, protocol compliance, and adverse event reporting at each site.
- Except in very unusual circumstances, each participating institution will order the agent(s) directly from the supplier. A participating site may order the agent(s) only after the initial IRB approval for the site has been forwarded to the Coordinating Center.

14. STATISTICAL CONSIDERATIONS

This is a standard 3+3 design Phase I study with an expansion cohort at the recommended Phase II dose to further explore the activity and safety of the regimen.

14.1 Study Design/Endpoints

Phase I:

The primary endpoint is to determine the MTD and DLT's of the combination of everolimus and pazopanib. Safety and incidence of dose-limiting toxicities will be the primary outcome parameters. All patients in a dose cohort will complete 28 days (1 cycle) of combination treatment prior to the treatment of any patient at a higher dose level. If a patient does not complete the 28 days of treatment for reasons that are clearly not adverse events related to treatment, then that patient will be replaced, up to three per dose level. If more than three patients need to be replaced on a dose level, then the reasons will be re-evaluated before continuing. There will be no intrapatient dose escalation. Pazopanib and everolimus will be escalated according to the standard 3+3 Phase I methodology and dose escalation rules (described in detail in Section 5.3.1). Once it is documented that the last patient in a cohort has completed 28 days of

therapy without evidence of excessive dose limiting toxicity, approval will be requested from the DF/HCC DSMB for dose escalation to the next dose level will occur. Successive cohorts of patients will be accrued to determine the maximum tolerated dose that results in <33% dose-limiting toxicities with the combination of everolimus and pazopanib in patients with metastatic kidney cancer. Up to six patients will be treated at the MTD before proceeding to the expansion cohort.

The assessment of safety will be based mainly on the frequency of adverse events and on the number of laboratory values that fall outside of pre-determined ranges. Toxicities will be summarized as number and percent of patients, separately by dose cohort. Other safety data (e.g. electrocardiogram, vital signs, special tests) will be considered as appropriate.

Adverse events will be summarized by presenting, for each dose cohort, the number and percentage of patients having any adverse event, having an adverse event in each body system, and having each individual adverse event. Any other information collected (e.g. severity or relatedness to study medication) will be listed as appropriate. Descriptive statistics will be calculated to characterize the disease and previous treatment features as well as the details of protocol therapy. Toxicities will be tabulated by grade for each dose cohort and overall for all patients accrued to the Phase I study.

The probabilities of dose escalation for various true DLT rates are summarized below:

	True Probability of DLT at Current Dose						
	0.10	0.20	0.30	0.40	0.50	0.60	0.70
Probability that dose is escalated	0.91	0.71	0.49	0.31	0.17	0.08	0.03

Expansion cohort:

The primary objective is to evaluate the safety and efficacy of the combination of pazopanib and everolimus in previously treated advanced urothelial carcinoma patients. The proportion of patients achieving objective response (OR) defined as complete or partial response per RECIST criteria as their best overall response is the primary endpoint. Simon's two-stage design is employed to minimize accrual if treatment with pazopanib and everolimus is not effective. Achieving objective response in this population has historically been difficult. There no FDA approved second line therapy for urothelial cancer. The only European approved therapy in this setting is Vinflunine with a response rate of 9%.⁽⁴⁸⁾ The null hypothesis for this study is assumed to be 10%.

Twenty-nine patients will be enrolled. Only eligible patients who start protocol therapy will be included in the response analysis. The first stage will accrue n=20 patients (n=18 eligible treated patients). If 3 or more objective responses are observed among the first stage cohort then an additional 9 patients will be accrued (n=8 eligible treated patients). If 5 or more responses are observed in the 26 eligible patients who started protocol therapy

then the combination of pazopanib with everolimus will be considered promising. The operating characteristics of this design are summarized below. If the true OR rate is 10%, the probability of stopping early at the first stage is 0.734 and the probability of accepting treatment for further study is 0.099 (Type I error). If the true OR rate is 30%, the probability of concluding the treatment is promising is 0.904 (power). Upon completion of the study, the true response rate will be estimated and an exact 90% confidence interval constructed.

	True Underlying Response Rate				
			20%	25%	30%
Probability of Stopping Early (<3/18)			0.271	0.135	0.060
Overall Probability of Concluding Effective ($\geq 5/29$)			0.577	0.781	0.904

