1. OBJECTIVES

1.1 Study Design

This is a Phase I study with an expansion cohort in advanced urothelial cancer patients. The Phase I portion of the study will be an open-label standard 3+3 dose escalation study to determine the maximum tolerated dose (MTD) of the combination of pazopanib (GW786034) and everolimus in patients with solid tumors who have no standard treatment options available. Starting doses will be set at everolimus 5 mg PO QD and pazopanib 400 mg PO QD. Cycle length will be 4 weeks. One dose de-escalation will be allowed if the MTD is exceeded in dose level 0 (indicated as dose level -1). Initial phase I testing identified pazopanib 400 mg PO daily and everolimus 5 mg PO daily as the MTD. Based on the phase I response data, an expansion cohort of 25 patients with metastatic urothelial cancer who have received prior chemotherapy, but no prior mTOR or VEGF inhibitors, will be enrolled.

The protocol is being amended to accrue urothelial carcinoma patients rather than kidney cancer patients in the expansion cohort given the significant unmet need in urothelial carcinoma and findings of significant activity of the regimen in at least a subset of urothelial carcinoma patients,

The primary endpoint of the expansion cohort will be objective response proportion with secondary endpoints including safety, progression-free survival, and duration of response.

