14.2 Sample Size/Accrual Rate

Phase I: 2 patients per month, with a maximum of 30 patients
Expansion cohort: 3 patients per month, with a maximum of 25 patients

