All patients who receive treatment will be included in toxicity analyses. A summary of the incidence of all treatment-related grade 3-5 toxicities will be provided as maximum grade by toxicity type and body system. Any other information collected (e.g. severity or relatedness to study medication) will be listed as appropriate. Overall maximum grade 3 or higher treatment-related toxicity rates in all treated patients will be calculated. The table below shows the 90% confidence intervals for 0, 2, 4, and 6 patients with grade 3 or higher toxicity in a total of 29 treated patients.

Observed Number of Patients with Grade \geq 3 Toxicity	Grade \geq 3 Toxicity Rate	90% Confidence Interval for True but Unknown Grade \geq 3 Toxicity Rate
0	0.0%	(0.0%, 9.8%)
2	6.9%	(1.3%, 20.2%)
4	13.8%	(4.9%, 28.9%)
6	20.7%	(9.4%, 36.8%)

Exploratory

Relevant somatic and germline alterations will be identified by adaptation and modification of discovery-oriented algorithms in common use at the Broad Institute and MSKCC. We will also apply a series of computational algorithms that predict neutral, detrimental or activating variants. Upon completion, we will deliver a list of somatic and germline variants that perturb cancer genes and associated cellular pathways, associated with response to therapy in this cohort. Relevant associations between mutation status and treatment outcome will be assessed on an exploratory basis, and relevant targeted sequencing may be performed in non-responders to further understand the association between response to study therapy and somatic alterations.

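### The 25-patient expansion cohort in Sections 1.1 and 14.2 cannot supply the 26 evaluable patients that the Section 14.1 decision rule needs, and the success row of the Section 14.1 table carries the wrong denominator

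*Combined protocol and SAP*

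**What the plan says.** All the places are in the combined protocol and SAP.

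- **Section 14.1, text.** "Twenty-nine patients will be enrolled". For stage 1: "The first stage will accrue n=20 patients (n=18 eligible treated patients"). With 3 or more responses, 9 more are accrued, expected to give 8 eligible treated patients. The final rule reads: "If 5 or more responses are observed in the 26 eligible patients who started protocol therapy", the combination is considered promising. Only eligible patients who start therapy enter the response analysis. The stated figures are type I error 0.099 and early stopping 0.734 at a true rate of 10%, and power 0.904 at 30%.
- **Section 14.1, table.** The stopping row is labelled "Probability of Stopping Early (<3/18") and the success row "Overall Probability of Concluding Effective ($\geq 5/29"). The success row prints 0.577, 0.781 and 0.904 at 20%, 25% and 30%.
- **Section 14.2.** "Expansion cohort: 3 patients per month, with a maximum of 25 patients".
- **Section 1.1.** It plans "an expansion cohort of 25 patients with metastatic urothelial cancer who have received prior chemotherapy".
- **Section 14.4, Toxicity.** The confidence intervals are for "grade 3 or higher toxicity in a total of 29 treated patients".

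**The concern.** The expansion cohort has two sizes. Sections 14.1 and 14.4 work with 29; Sections 1.1 and 14.2 work with 25, and Section 14.2 states it as a maximum. Under that maximum the final analysis described in Section 14.1 can never take place, because it needs 26 evaluable patients. A team that follows the cap would have to apply the rule to fewer patients than it was designed for, with error rates that the plan does not give.

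The rule that declares success also has two denominators: 26 in the text and 29 in the table. The row above uses 18, the evaluable stage 1 count and not the 20 enrolled, so the 29 cannot be read as a convention of labelling rows by enrolment. At stake is whether the stated 0.099 and 0.904 describe the trial that will be run.

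**Working it through.** **Inputs (Section 14.1).** Null rate 10%; alternative 30%; stage 1 with 18 evaluable, continue at 3 or more; final total 26 evaluable, success at 5 or more; enrolment 20 then 9.

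**Formulas.** With evaluable counts n1 at stage 1 and n in total, and X1 ~ Bin(n1, p):

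- P(stop) = P(X1 ≤ 2)
- P(success) = Σ over x ≥ 3 of P(X1 = x) × P(Bin(n − n1, p) ≥ 5 − x), where the second factor is 1 once x ≥ 5.

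**Step 1. Reproduce the plan's figures (n1 = 18, n = 26).**

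- At 10%: 0.1680 × 0.1869 + 0.0700 × 0.5695 + 0.0282 = 0.0314 + 0.0399 + 0.0282 = 0.0995 (unrounded 0.09946; printed as 0.099).
- At 30%: 0.1046 × 0.7447 + 0.1681 × 0.9424 + 0.6673 = 0.0779 + 0.1584 + 0.6673 = 0.9037 (printed as 0.904).
- At 20% and 25%: 0.5769 and 0.7808 (printed as 0.577 and 0.781).
- P(stop): 0.7338 at 10%, and 0.2713, 0.1353, 0.0600 at 20%, 25%, 30%.

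Every legible printed value is matched.

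**Step 2. Test the label (n1 = 18, n = 29, cut-offs 3 and 5).**

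| True rate | 18 then 26 | 18 then 29 | Printed |
|---|---|---|---|
| 10% | 0.099 | 0.127 | 0.099 |
| 20% | 0.577 | 0.636 | 0.577 |
| 25% | 0.781 | 0.822 | 0.781 |
| 30% | 0.904 | 0.925 | 0.904 |

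A search over stage 1 sizes 10 to 27, totals up to 35, stage 1 cut-offs 1 to 5 and final cut-offs up to 8 found 18/26 with cut-offs 3 and 5 as the only design matching the success row to about 0.001. The values belong to 26.

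**Step 3. What a cap of 25 would do.** At the planned yield, 25 × 26/29 = 22.4 evaluable patients are expected. The plan gives no stage split for 25, so assume 20 then 5 enrolled, cut-offs 3 and 5 unchanged, and independent attrition q. A patient then counts as an evaluable responder with probability p(1 − q). The averages follow from the same formula with n1 = 20, n = 25 and p(1 − q) in place of p. For example, at q = 3/29, 0.30 × 26/29 = 0.2690.

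| Attrition q | Type I error at 10% | Power at 30% |
|---|---|---|
| 0 | 0.095 | 0.905 |
| 5% (assumed) | 0.080 | 0.875 |
| 3/29 (the plan's) | 0.066 | 0.836 |
| 15% (assumed) | 0.055 | 0.795 |

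**Step 4. Other evaluable counts with 29 enrolled (secondary).** Cut-offs unchanged, type I error and power are 0.109 and 0.913 at 18/27, 0.094 and 0.891 at 17/26, and 0.141 and 0.945 at 20/29, which requires no attrition at all. Averaged over attrition of 3/29 with 20 then 9 enrolled, they are 0.100 and 0.898.

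**The case against.** The label is editorial. The text states the rule in full, the threshold is 5 responses under either reading, and every printed probability is right. That stands. A reader might infer from the label that the power calculation is wrong, or that the trial will run at a type I error of 0.127. Neither is supported: the calculation is that of the text's rule, and 18 then 29 does not arise from accruing 20 then 9 unless late-evaluable stage 1 patients are added after an interim look on 18.

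The conflict between 25 and 29 is real, but the loss of power rests on assumptions: the cap is enforced, the split is 20 then 5, and attrition is independent. If all 25 are evaluable under that split, power is 0.905. With 18 then 25 evaluable it is 0.892. This also stands, so 0.836 is a conditional figure. It does not remove the contradiction, since no reading of 25 gives 26.

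A reader might also infer that having no rule for counts other than 18 and 26 seriously inflates the type I error, because Section 14.5.2 bases conclusions on all eligible treated participants. The plan's own attrition does not bear this out: over-runs and under-runs average to 0.100 against 0.099, and 0.141 needs every enrolled patient to be evaluable. The omission is mostly missing detail.

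**Conclusion.** Two statements are wrong as written. First, 25 in Sections 1.1 and 14.2 contradicts the 29 enrolled and 26 eligible treated in Section 14.1 and the 29 treated in Section 14.4. This is the main point. If the cap governed, power at 30% would be about 0.836 at the plan's attrition (0.875 to 0.795 over an assumed 5% to 15%), under the assumptions of Step 3. Second, the success row should refer to 26. This certainty rests on exact reproduction and needs no assumption, but it is a labelling error and changes no stated probability.

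The documents do not show that the trial as designed in Section 14.1 is underpowered or has an inflated error rate. With 29 enrolled and the text's rule, 0.099 and 0.904 are correct at 18 and 26. The point should be fixed, because it concerns the primary decision rule and the correction costs almost nothing.

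**What to change.** 1. Change Sections 1.1 and 14.2 to 29 enrolled (26 eligible treated). If 25 is the intended maximum, restate the stage sizes, cut-offs, type I error and power for 25 in Section 14.1, and redo the Section 14.4 toxicity table.
2. Relabel the success row as 5 or more of 26.
3. Optional and minor: add a sentence to Section 14.1 saying that 0.099 and 0.904 hold at exactly 18 and 26 evaluable patients, that cut-offs 3 and 5 apply at the actual counts whether above or below plan, and that the attained type I error and power will be reported.

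Deciding on the first 18 and first 26 eligible treated patients should not be presented as a guarantee of 0.099 and 0.904. With evaluability 26/29 per patient and 20 then 9 enrolled, the chance of at least 18 in stage 1 and at least 26 in total is 0.574, so one or both counts fall short with probability 1 − 0.574, about 0.43.

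The cost, with 29 kept, is two corrected numbers, one label and at most one sentence, with no patients beyond the 29 already planned and no new data. The small downside of item 3 is that the reported error rates may be slightly less favourable than those now stated.

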14.2 Sample Size/Accrual Rate

Phase I: 2 patients per month, with a maximum of 30 patients
Expansion cohort: 3 patients per month, with a maximum of 25 patients

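### Sections 1.1 and 14.2 hold the expansion cohort to 25 patients, but the two-stage design in Section 14.1 enrols 29 to analyse 26, so the final decision rule cannot be run under the cap

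*Combined protocol and SAP*

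**What the plan says.** The expansion cohort's size is given in four places in the combined protocol and SAP.

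- Section 14.2 (Sample Size/Accrual Rate): "Expansion cohort: 3 patients per month, with a maximum of 25 patients".
- Section 1.1 (Study Design): "an expansion cohort of 25 patients with metastatic urothelial cancer who have received prior chemotherapy".
- Section 14.1 (Study Design/Endpoints, expansion cohort): "Twenty-nine patients will be enrolled". It accrues 20 patients to obtain 18 eligible treated. If at least 3 of them respond, it accrues 9 more to obtain 8 more eligible treated. The regimen is called promising if at least 5 of the resulting 26 respond.
- Section 14.4 (Toxicity) gives intervals for patients with "grade 3 or higher toxicity in a total of 29 treated patients".

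Section 14.1 also fixes the analysis set: "Only eligible patients who start protocol therapy will be included in the response analysis". It states an early stopping probability of 0.734 and a type I error of 0.099 at a 10% response rate, and power of 0.904 at 30%.

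**The concern.** All four statements concern the same cohort and are current operative text. The 25 cannot be read as the evaluable count, because that count is 26. With no more than 25 enrolled, the 26-patient final analysis can never take place, and the final boundary cannot be applied as written.

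The number enrolled is a basic parameter of the primary analysis. If sites follow Section 14.2, accrual ends during stage 2, 29 − 25 = 4 patients short, and someone must decide how to read the boundary after responses are known in an open-label single-arm study. If they follow Section 14.1, the trial enrols 4 patients beyond the protocol's own maximum. In the first case the printed power, type I error and toxicity intervals describe a design that was not run.

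**Working it through.** **Inputs (Section 14.1).** Stage 1: n1 = 18, continue if X1 ≥ 3. Success: at least 5 responses in total among n. Null rate 10%, alternative 30%.

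**Formula.** With m = n − 18 evaluable patients in stage 2 and X2 ~ Bin(m, p),

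P(success) = P(X1=3)·P(X2≥2) + P(X1=4)·P(X2≥1) + P(X1≥5).

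**Stage 1 terms, X1 ~ Bin(18, p).**

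| p | P(X1≤2) | P(X1=3) | P(X1=4) | P(X1≥5) |
|---|---|---|---|---|
| 0.10 | 0.7338 | 0.1680 | 0.0700 | 0.0282 |
| 0.30 | 0.0600 | 0.1046 | 0.1681 | 0.6674 |

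**Step 1: reproduce the plan (n = 26, m = 8).**

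- p = 0.10: 0.1680 × 0.1869 + 0.0700 × 0.5695 + 0.0282 = 0.0314 + 0.0399 + 0.0282 = 0.0995 (0.09946 unrounded; stated 0.099).
- p = 0.30: 0.1046 × 0.7447 + 0.1681 × 0.9424 + 0.6674 = 0.0779 + 0.1584 + 0.6674 = 0.9037 (stated 0.904).
- Early stopping at 10% is 0.734, as stated. The tabulated 0.577 at 20% and 0.781 at 25% also reproduce.

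Counting every enrolled patient does not reproduce the stated figures: 18 then 29 gives 0.127 and 0.925, and 20 then 29 gives 0.141 and 0.945. The printed characteristics belong to 26 evaluable patients.

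**Step 2: how many are evaluable under a cap of 25?** The plan's own yields are 18/20 = 0.900 overall in stage 1, 8/9 = 0.889 in stage 2 and 26/29 = 0.897 in total. Then 25 × 0.897 = 22.4, so 22 or 23. The most favourable case is 25, with nobody lost.

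**Step 3: the same rule (≥3 of 18, then ≥5 in total) at those sizes.**

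| Evaluable n | m | Type I error (10%) | Power (30%) |
|---|---|---|---|
| 26 (plan) | 8 | 0.099 | 0.904 |
| 25 | 7 | 0.090 | 0.892 |
| 24 | 6 | 0.080 | 0.876 |
| 23 | 5 | 0.071 | 0.857 |
| 22 | 4 | 0.061 | 0.832 |

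As an example, for n = 22 at 30%: 0.1046 × 0.3483 + 0.1681 × 0.7599 + 0.6674 = 0.0364 + 0.1277 + 0.6674 = 0.8315.

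The loss of power is 0.904 − 0.892 = 1.2 points with 25 evaluable, and 4.7 to 7.2 points with 23 or 22. At a true rate of 20%, the chance of a positive conclusion falls from 0.577 to 0.489 (n = 23) or 0.452 (n = 22).

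**Step 4: toxicity intervals.** For 0 events the exact 90% upper limit is 1 − 0.05^(1/N). For N = 29 this is 9.8%, as tabulated. For N = 25 it is 11.3%. For 6 events the upper limit moves from 36.8% to 42.0%.

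**The case against.** No calculation in the plan is wrong: the stated operating characteristics are correct for 26 evaluable patients. Section 14.1 specifies the design in full and Section 14.4 repeats the 29, so the 25 may be wording that was never updated. Only Section 14.2 calls 25 a maximum; Section 1.1 gives it as a size. Type I error falls under the cap, so the stated limit still holds conservatively. The loss of power depends on evaluability. One dose makes a patient evaluable for response (Sections 10.1.1 and 14.5.2) and eligibility is checked before registration, so few patients need be lost, and with none lost the shortfall is 1.2 points. The cap also matters only if stage 1 passes: at a 10% response rate the trial stops first with probability 0.734. Finally, 25 does not in itself rule out 90% power: judging stage 1 at 20 evaluable, with all 25 evaluable at the end, gives type I error 0.095 and power 0.905.

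These points limit the size and the wording, and they are accepted. They do not remove the contradiction. That the 25 is leftover text is an inference that the document does not state. The 20-then-25 rule is not the one written, and it allows no losses, whereas the plan itself allows about 10%. The cap does its harm when the regimen works: at a 30% response rate stage 1 is passed with probability 0.940.

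**Conclusion.** The concern holds. The protocol gives two incompatible sizes for the cohort on which its primary decision rests, and under the smaller one the rule of 5 or more in 26 cannot be applied. If the 5-response threshold were kept with 25 enrolled, power at 30% would lie between 0.832 (22 evaluable) and 0.892 (all 25 evaluable), against the stated 0.904. Type I error would lie between 0.061 and 0.090, against 0.099. These figures assume that stage 1 is judged at 18 evaluable patients, as written. The lower end also assumes the plan's own evaluable fraction of about 90%. If accrual follows Section 14.1, the printed statistics stand, and the fault is that enrolment exceeds the stated maximum. The effect on the toxicity table is small and touches no decision rule. This must be fixed because the authorised sample size cannot be determined from the document.

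**What to change.** Change Sections 1.1 and 14.2 to 29 enrolled (20, then 9) for 26 eligible treated. That matches Section 14.1 and the toxicity table and leaves the design unchanged; the cost is two wording corrections. In the same amendment, correct the success row of the operating-characteristics table in Section 14.1, which gives 29 as the denominator although its probabilities reproduce with 26.

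If 25 is the real ceiling, restate the stage sizes, both boundaries, type I error, power and the toxicity table for the 22 to 25 evaluable patients it can deliver, and do so before stage 2 responses are known. Keeping the present stage 1 size and thresholds would mean declaring power of 0.83 to 0.89 in place of 0.904.
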